6.4.6.4 Disease specific tumour marker samples (CA-125)

As part of the routine safety blood samples, all patients will supply blood sample for CA-125 (2 mL) for assessment at the beginning of each 28 day period prior to the patient receiving study treatment.

It is important to follow the assessment schedule as closely as possible. If CA-125 assessment is performed outside of scheduled visit ± 1 week window interval, every attempt should be made to assess the CA-125 at the scheduled time points. Patients will be evaluated until objective disease progression, based on progressive serial elevation of serum CA-125 according to the modified Gynecologic Cancer InterGroup criteria GCIG criteria (note GCIG criteria is not validated for this trial population) (see Section [11.1.2.2](#)).

Further assessment of CA 125 post serological progression will be at the discretion of the investigator according to local clinical practice.

For blood volume see Section [7.1](#).

Date 05 November 2021

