7. BIOLOGICAL SAMPLING PROCEDURES

7.1 Volume of blood

The volume of blood that will be drawn from each patient will vary, dependent upon the length of time that the patient remains in the trial and on treatment. However the volume of blood to be drawn from each patient during screening and up to Day 29 should not exceed 110 mL.

The total volume of blood to be drawn from each patient in the study, assuming they complete screening, 6 months of treatment, a treatment discontinuation visit and the 30-day follow-up visit, should not exceed 195 mL. Beyond this, blood draws will be as per the schedule laid out in [Table 87.1](#).

Safety laboratory assessments will be performed locally at each centre's laboratory by means of their established methods. The number of samples/blood volumes is therefore subject to site-specific change.

Revised Clinical Study Protocol
Drug Substance AZD2281
Study Code D0818C00001
GOG Code GOG-3004

[REDACTED]
Date 05 November 2021

Extra blood samples may also be collected if, for example, additional samples are required for repeat safety assessments.

Date 05 November 2021

The estimated total volume of blood that will be drawn from each patient in this study is as follows:

Table 8 Estimated maximum volume of blood to be drawn from each patient

Assessment		Sample volume (mL)	No. of samples - screening	No. of samples -month 1 (including day 29)	Months 2-6	Treatment discontinuation visit and 30 day follow-up visit	Objective radiological disease progression	Total volume (mL)
Safety	Clinical chemistry (locally assessed)	5	1	5	1(x4)	1(x2)		60
	Haematology (locally assessed)	5	1	5	1(x4)	1(x2)		60
Whole blood sample: Prospective Myriad BRCA test for patients with unknown BRCA status or for confirmation of BRCA status for those with previous results)		9	1					9
[REDACTED]		9	1					9
Blood sample for biomarker analysis (e.g. cfDNA)		12		1			1	24
Blood cytogenetic analysis		Site dependent	Depends on the blood smear result					

Date 05 November 2021

Assessment	Sample volume (mL)	No. of samples - screening	No. of samples -month 1 (including day 29)	Months 2-6	Treatment discontinuation visit and 30 day follow-up visit	Objective radiological disease progression	Total volume (mL)
Serum pregnancy test	Site dependent	Site may use urine instead	Site may use urine instead				
Blood sample for CA-125 (locally assessed)	2	3	1(x2)	1x4	1(x1) (only treatment discontinuation visit)		20
Optional exploratory pharmacogenetics	9		1				9

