11.1.2.2 Time to earliest progression by RECIST 1.1 or CA-125 or death

Progression or recurrence based on serum CA-125 levels will be defined on the basis of a progressive serial elevation of serum CA-125, according to the following modified GCIG criteria (note GCIG criteria is not validated for this trial population):

- Patients with elevated CA-125 pre-treatment (i.e. greater than the upper limit of normal (ULN)):-
 - (a) If CA-125 does not fall to within the normal range whilst on treatment then there must be evidence of CA-125 greater than, or equal to, 2 times the nadir value in the 28 day period before day 1 on 2 occasions at least 1 week apart.
 - (b) Where CA-125 does fall to within the normal range whilst on study treatment (and the patient has not already progressed by way of (a) above) then there must be evidence of CA-125 greater than, or equal to, 2 times the ULN on 2 occasions at least 1 week apart.

- Patients with CA-125 in the normal range pre-treatment must show evidence of CA-125 greater than, or equal to, 2 times the ULN on 2 occasions at least 1 week apart. CA-125 progression will be assigned the date of the first measurement that meets the criteria as noted.

Time to progression by RECIST or CA-125 progression or death is defined as the time from randomisation to the earlier date of RECIST or CA-125 progression or death by any cause. Patients without a CA-125 progression or a RECIST progression who are still alive at the time of analysis will be censored at their last evaluable RECIST assessment or their last available CA-125 measurement, whichever is the most recent at the time of the analysis. If a patient progresses or dies after two or more missed RECIST and CA-125 assessments, then the patient will be censored at the time of their last evaluable assessment. If only one assessment is missing during this period, no censoring is required.

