3.2.7 Time to earliest progression by RECIST or CA-125 or death

Progression or recurrence based on serum CA-125 levels will be defined on the basis of a progressive serial elevation of serum CA-125, according to the following modified Gynecologic Cancer Intergroup (GCIG) criteria (note GCIG criteria is not validated for this trial population):

• For patients with elevated CA-125 on or before the date of randomisation (i.e. greater than the upper limit of normal (ULN)):

- (a) If CA-125 does not fall to within the normal range post-randomisation then there must be evidence of CA-125 greater than, or equal to, 2 times the nadir value in the 28 day period before day 1 on 2 occasions at least 1 week apart
- (b) Where CA-125 does fall to within the normal range post-randomisation then there must be evidence of CA-125 greater than, or equal to, 2 times the ULN on 2 occasions at least 1 week apart
- Patients with CA-125 in the normal range on or before the date of randomisation and no results greater than ULN on or before the date of randomisation must show evidence of CA- 125 greater than, or equal to, 2 times the ULN on 2 occasions post-randomisation at least 1 week apart.
- CA-125 progression will be assigned the date of the first measurement that meets the above criteria.

Time to progression by RECIST or CA-125 progression or death is defined as the time from randomisation to the earlier date of RECIST or CA-125 progression or death by any cause.

Patients without a CA-125 progression or a RECIST progression who are still alive at the time of analysis will be censored at the time of their last evaluable RECIST assessment or their last available CA-125 measurement, whichever is the earliest at the time of the analysis. Since CA-125 is assessed more frequently than RECIST the two missed visit rule is based upon the RECIST schedule. Therefore if a patient dies, has RECIST progression or has CA-125 progression after two or more missed RECIST assessments, then the patient will be censored using at the last evaluable RECIST assessment where CA-125 was also collected. This will be defined as a RECIST assessment where the date of CA-125 sample is +/- 11 days (note the earliest date of the RECIST/CA-125 assessment will be used).

If only one assessment is missing during this period, no censoring is required. Patients that do not have any evaluable RECIST assessments or any CA-125 results post-randomisation will be censored at the date of randomisation.

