6 CHANGES OF ANALYSIS FROM PROTOCOL

All efficacy and HRQoL will be analysed using FAS.

Section 3.2.1 Progression free survival

Added clarification that according to the RECIST 1.1 guidelines an overall visit response of PD also requires an absolute increase of > 5 mm in the sum of the diameters of the target lesions.

Section 3.2.7 Time to earliest progression by RECIST or CA-125 or death Derivations will be relative to randomization (CSP states start of study treatment). Also, censoring will use the earliest of the last evaluable RECIST assessment or the last available CA-125 measurement (CSP states most recent).

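### For time to RECIST or CA-125 progression, SAP 3.2.7 censors at the earlier of last scan and last CA-125 but counts later events, so censoring depends on the outcome

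*SAP*

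**What the plan says.** SAP 3.2.7 defines the endpoint as the time from "randomisation to the earlier date of RECIST or CA-125 progression or death by any cause". Living patients without either kind of progression "will be censored at the time of their last evaluable RECIST assessment or their last available CA-125 measurement, whichever is the earliest".

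A late event is set aside only if two or more scans were missed before it. The SAP gives its reason: "Since CA-125 is assessed more frequently than RECIST the two missed visit rule is based upon the RECIST schedule". A gap in CA-125 alone never removes an event.

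Protocol 11.1.2.2 uses the same two dates but censors at the later one, "whichever is the most recent at the time of the analysis". Its missed-visit rule refers to RECIST and CA-125 assessments together. SAP Section 6 lists the switch from most recent to earliest as a change from the protocol and gives no reason.

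Scans continue after study drug stops, until RECIST progression (protocol 6.3.2). CA-125 is described in protocol 6.4.6.4 as part of the safety bloods, "for assessment at the beginning of each 28 day period prior to the patient receiving study treatment". The same section also says evaluation runs until objective progression. The off-treatment schedule, Table 4, is redacted.

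**The concern.** Events and censoring use different cut-offs. A patient scanned clear after her last CA-125 loses the follow-up that those scans provide. The same patient with a new lesion on one of those scans keeps it and becomes an event. Event-free patients leave the risk set early, while later events stay in the numerator. The estimated late hazard is then too high and the Kaplan-Meier curve too low.

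The patients most exposed, if CA-125 sampling ends with study drug, are those who stop at two years with no evidence of disease. They form the long-term event-free group, and their scans continue. The endpoint is a named secondary objective, analysed with the same log-rank, Cox and Kaplan-Meier methods as PFS, so both the curve and the hazard ratio would be reported.

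**Working it through.** **The plan's own figure.** Neither document gives a figure for this endpoint, so the PFS design anchors the simulation. Events for 90% power at HR 0.62, 2:1, two-sided 5%: (1.960 + 1.282)² / [(2/3)(1/3)(ln 0.62)²] = 10.51 / (0.2222 × 0.2285) = 206.9, against 206 stated. The olaparib median is 13/0.62 = 21.0 months, which matches 13 + 8.

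**Dated example, if CA-125 stops with drug.** Drug and last CA-125 end at week 104, scans run to week 156, and data cut-off is week 160.
- All scans clear: censored at week 104.
- New lesion at week 156: event at week 156. The previous scan was at week 144, so none was missed and the event stands.
- The 156 − 104 = 52 weeks count as at risk only if she has an event.

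**Dated example, on drug.** Last scan at week 96, CA-125 at weeks 100 and 104, cut-off at week 106. Event-free, she is censored at week 96. If CA-125 progression is first met at week 100 and confirmed at week 104, she is an event at week 100. This mismatch is at most about one scan interval: 12 weeks to week 156, 24 weeks after.

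**Simulation.**
- From the documents: 391 patients, 2:1, exponential times with a 13-month placebo median, HR 0.62, the scan schedule, CA-125 every 4 weeks on drug, and 18-month recruitment.
- Assumed: uniform accrual; 80% of progression-free patients stop drug at week 104; toxicity stops of 10% on olaparib and 2% on placebo; 60% of progressions preceded by CA-125 by 0 to 16 weeks; no deaths without progression.
- Replicates: 60 per scenario.

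The true 36-month event-free proportions under the model are 0.5^(36 × 0.62/13) = 30.4% on olaparib and 0.5^(36/13) = 14.7% on placebo.

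| CA-125 off drug | Cut-off | HR: earlier date | HR: most recent | 36-month event-free, earlier date (olaparib / placebo) | Same, most recent |
|---|---|---|---|---|---|
| Stops | 196 events (about month 29) | 0.636 | 0.620 | not reached | not reached |
| With each scan | 196 events | 0.640 | 0.640 | not reached | not reached |
| Stops | Last patient + 36 months | 0.670 | 0.618 | 17.2% / 8.6% | 30.0% / 14.3% |
| With each scan | Last patient + 36 months | 0.626 | 0.626 | 29.5% / 13.7% | 29.5% / 13.7% |

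If CA-125 stops with drug, the hazard ratio shift is 0.636 − 0.620 = 0.016 at 196 events and 0.670 − 0.618 = 0.052 at the later cut-off. The 36-month estimate at the later cut-off falls by 12.8 points on olaparib and 5.7 on placebo.

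At 196 events no simulated patient has 36 months of follow-up, so a 36-month value there would only be the end of the curve. At 24 months, with CA-125 stopping, the estimates are 42% against 45% on olaparib and 26% against 28% on placebo. If CA-125 is drawn with each scan, the end of the curve at 196 events is lower by about 1.5 points (38.6% against 40.1% on olaparib).

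A repeat with 150 replicates gave the same pattern, with a shift nearer 0.04 at the later cut-off. With a true HR of 0.35 and CA-125 stopping, the later cut-off gives 0.406 against 0.352. Under the null the hazard ratio is 1.00 with the earlier date and 0.99 with the most recent.

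**The case against.** **CA-125 may well continue off drug.** Protocol 6.4.6.4 says evaluation runs until objective progression. SAP 3.2.7 calls CA-125 the more frequent measure without limiting that to time on drug. Protocol 3.1 names a rising CA-125 as a trigger for off-drug scans and keeps 12-weekly visits. Table 8 counts CA-125 at the discontinuation visit but not at the 30-day visit; it is only a blood-volume estimate around six months of treatment, with no column for routine follow-up. Other text points the opposite way. Protocol 6.4.6 schedules safety samples by Tables 1 to 3, while scans follow Tables 3 and 4, and SAP 3.2.7 speaks of a scan at which CA-125 was also collected, which implies some without. Neither side is decisive. A reader might infer that patients off drug stay at risk only if they progress. The documents do not support that as a fact: it needs CA-125 to stop first, deaths also count, and events after two missed scans are censored.

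**The large figures need a late cut-off.** The endpoint is analysed with primary PFS, at about 196 events or last patient plus 36 months, whichever comes first. Under the design medians 196 events arrive near month 29, where the effect is small. This stands. A larger treatment effect would delay the trigger.

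**The earlier date has a rationale.** It confines event-free time to the period covered by both measures. That would be coherent if events were confined in the same way, but they are not.

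**The change is disclosed and the endpoint is supportive.** Both are true and limit the importance. Disclosure does not remove the mismatch.

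**Conclusion.** The asymmetry is in the SAP text and does not depend on any assumption: event-free patients are cut at the earlier date and events are not. Its size does depend on assumptions.
- **CA-125 continues with scans:** no change in the hazard ratio, and late Kaplan-Meier estimates lower by about 0 to 3 points.
- **CA-125 stops with drug, 196-event cut-off:** the hazard ratio moves toward 1 by 0.01 to 0.02.
- **CA-125 stops with drug, last patient plus 36 months:** the hazard ratio moves toward 1 by about 0.05, with 36-month event-free about 17% instead of 30% on olaparib and 9% instead of 14% on placebo.

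The stopping pattern, CA-125 lead time and accrual shape are assumed, and the redacted Table 4 leaves open which case applies. A reader might also infer that the rule flatters olaparib or touches the confirmatory results. It does neither: the shift is toward 1, there is none under the null beyond simulation noise, and the PFS, PFS2 and OS tests do not use this rule.

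**What to change.** In SAP 3.2.7, censor living, event-free patients at the most recent of last evaluable RECIST assessment and last CA-125, as in protocol 11.1.2.2, and delete the matching line in Section 6. State the off-treatment CA-125 schedule beside the rule so that a reader can judge how much it matters.

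SAP Section 5 shows that the primary PFS analysis came before this February 2022 version, and this endpoint was due at that analysis. If it has already been analysed, leave the reported result and add a supplementary analysis under the protocol rule, labelled as such.

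The editing cost is one word in 3.2.7 and one sentence in Section 6. The statistical cost is that the most recent date can rest on one measure alone. If CA-125 is not drawn off drug, CA-125-only progressions after stopping go unseen, possibly more often on olaparib if more of those patients stop without progression. The report should say so.

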3.2.8 Best overall RECIST response (BoR)

Best overall response (BoR) is calculated based on the overall visit responses from each RECIST assessment (Table 4). It is the best response a patient has had following randomisation but prior to starting any subsequent cancer therapy and prior to RECIST progression or the last evaluable assessment in the absence of RECIST progression.

Categorisation of BoR will be based on the RECIST criteria using the following response categories: complete response (CR), partial response (PR), stable disease (SD), No Evidence

of Disease (NED; applies only to those patients entering the study with no disease at baseline), progressive disease (PD) and not evaluable (NE).

Best overall response will be programmatically derived from the investigator data.

For determination of a best response of SD, the earliest of the dates contributing towards a particular overall visit assessment will be used. SD should be recorded at least 12 weeks +/- 1 week, i.e. at least 77 days (to allow for the assessment window), after randomisation. For CR/PR, the initial overall visit assessment which showed a response will use the latest of the dates contributing towards a particular overall visit assessment.

For patients whose progression event is death, BoR will be calculated based on data up until the last evaluable RECIST assessment prior to death.

For patients who die with no evaluable RECIST assessments, if the death occurred \leq 25 weeks (i.e. 24 weeks ± 1 week) after randomisation then BoR will be assigned to the progression (PD) category. For patients who die with no evaluable RECIST assessments, if the death occurred \geq 25 weeks (i.e. 24 weeks ± 1 week) after randomisation then BoR will be assigned to the non-evaluable (NE) category.

Progression events that have been censored due to them being more than two missed visits after the last evaluable assessment will not contribute to the BoR derivation.

A patient will be classified as a responder if the RECIST criteria for a CR or PR are satisfied at any time prior to RECIST progression or the last evaluable assessment in the absence of RECIST progression, up to the earliest of the defined analysis cut-off point or the start of subsequent therapy. For each treatment group, the objective response rate (ORR) is the number of patients with a CR or PR post-baseline divided by the number of patients in the group in the FAS with measurable disease at baseline. Only patients with measurable disease at enrolment can achieve an objective response of CR or PR.

Duration of response will be defined as the time from the date of first documented response until date of documented progression or death in the absence of disease progression. The end of response should coincide with the date of progression or death from any cause used for the PFS endpoint. The time of the initial response will be defined as the latest of the dates contributing towards the first visit response of PR or CR. If a subject does not progress following a response, then their duration of response will use the PFS censoring time.

Time to onset of objective response is defined as the time from the date of randomisation until the date of first documented response. The date of first documented response should coincide with that used for the RECIST 1.1 BoR endpoint. Time to response will not be defined for those patients who do not have documented response.

The disease control rate (DCR) is defined as the percentage of patients who have at least one confirmed visit response of CR or PR or have demonstrated SD or NED for at least 23 weeks

(i.e. 24 weeks ± 1 week) prior to any evidence of progression. In the case of SD and NED, follow up assessments must have met the SD or NED criteria for a minimum interval of 23 weeks following randomisation.

3.3 Patient Reported Outcome (PRO) Variables

3.3.1 FACT-O

Patient reported health-related quality of life (HRQoL) will be assessed using the Functional Assessment of Cancer Therapy – Ovarian (FACT-O) questionnaire (Basen-Enquist K et al 2001). The FACT-O is composed of the following sub-scales: physical, social/family, emotional, and functional well-being as well as the additional concerns scales consisting of specific ovarian cancer symptoms.

The endpoint for HRQoL analysis will be the Trial Outcome Index (TOI), (Cella D et al 1993) an established single targeted index derived from the FACT-O questionnaire and it is considered to target the most relevant symptoms together with function and physical well-being and can be directly related to signs and symptoms and AEs. The TOI is composed of the following scales of the FACT-O: physical and functional well-being and additional concerns (ovarian cancer subscale).

Data relating to the FACT-O will be self-reported through patient questionnaires according to the study plan. Patients will be asked to report their HRQoL over the course of the previous 7 days. All patients will be asked to complete the FACT-O. The FACT-O questionnaire will be administered at baseline, at Day 29, then in line with the RECIST assessments every 12 weeks (+/- 7 days) for 156 weeks, then every 24 weeks (+/- 7 days) up to the data cut off for the primary analysis. In addition, HRQoL questionnaires will be collected at the discontinuation of study treatment visit and 30 days post last dose. Patients who had RECIST 1.1 disease progression will complete the questionnaires during the 12 weekly survival follow-up visits either in person or over the phone.

The Trial Outcome Index (TOI) score will be derived from the sum of the scores of three of the derived subscale scores; physical well-being (7 items), functional well-being (7 items), and ovarian cancer subscale (11 items) of the FACT-O questionnaire version 4. The total FACT-O score will also be calculated which is made up of the sum of the individual subscale scores: physical well being (PWB), social well being (SWB), emotional well being (EWB), functional well being (FWB) and ovarian cancer subscale (Additional Concerns) (11 items).

The scores will be derived in accordance with the FACT-O Scoring Manual. A number of items are negatively stated and need to be reversed by subtracting the response from "4". The scoring manual identifies that the following items need to be reversed prior to summarising: GP1-7, GE1, GE3-6, O1-3, C2, and B5. After reversing proper items, scores are summarised and multiplied by the number of items in the domain. For each subscale (domain), if less than 50% of the subscale items are missing, the subscale score will be divided by the number of non-missing items and multiplied by the total number of items on the subscale. If at least 50%

of the items are missing, that subscale also will be treated as missing. The reason for any missing assessment will be identified. If data are missing at random, the above techniques will be used. If there is evidence that the missing data are systematic, missing values will be handled to ensure that any possible bias is minimised. The TOI score ranges from 0-100 and the FACT-O from 0-152. For all Functional Assessment of Chronic Illness Therapy (FACIT) scales and symptom indices, a higher score indicates a higher HRQoL.

The actual change from baseline in TOI score will be derived for each visit where there is available data. For example; at visit X, the calculation will be (TOI score at visit X – baseline TOI score). Actual change from baseline for the individual FACT-O subscale scores will be calculated in a similar way. The baseline score is defined as last non-missing score prior to dosing with study treatment (olaparib or placebo). Any questionnaires completed on day 1 of dosing will be considered pre-dose.

A change of at least 10 points in TOI will be considered as a clinically relevant or a minimally important difference (Osobo et al 2005).

The threshold for a clinically important change is outlined below (Table 5):

Table 5 Health-Related Quality of Life

Score	Change from baseline	Visit response
TOI	≥+10	Improved
	≤-10 or "Subject too heavily affected by symptoms of disease under investigation" is answered as the reason for not completing HRQoL at visit.	Worsened
	Otherwise	No change

Best overall TOI improvement (in absence of starting any subsequent cancer therapy) will be defined as a change from baseline in the TOI of + 10 points or more (Osoba et al 2005) sustained for at least 28 days, the denominator consisting of a subset of the FAS population who have baseline TOI. It will be derived as the best symptom improvement response the patient achieved, based on evaluable HRQoL data collected from randomisation up to the earliest of starting any subsequent cancer therapy or death. Therefore, at the conclusion of the trial, the following criteria, will be used to assign a best overall score response based on the individual visit responses (Table 6).

Table 6 Health-Related Quality of Life: Change rates - overall score

Best overall TOI score response	Criteria
Improved	Two visit responses of "improved" a minimum of 28 days apart without an intervening visit response of "worsened"
No change	Does not qualify for overall score response of "improved". Two visit responses of either "no change" or "improved and "no change" a minimum of 28 days apart without an intervening visit response of "worsened"
Worsened	Does not qualify for overall score response of "improved" A visit response of "worsened" without a subsequent response of "improved" or "no change" within 28 days.
Other	Does not qualify for one of the above.

In the calculation of the proportion of patients that have a response of Improved, No Change or Worsened, the denominator used in the calculation will use the number evaluable patients with a TOI score at baseline.

Summary measures of overall compliance and compliance over time will be derived for the FACT-O questionnaire. These will be based upon:

- Received forms = number of FACT-O forms received back plus the number not received back where the reason was 'Subject too heavily affected by symptoms of disease under investigation'.
- Expected forms = number of patients still under HRQoL follow-up at the specified assessment time excluding patients in countries with no available translation. For patients that have progressed, the latest of progression and safety follow-up will be used to assess whether the patient is still under HRQoL follow-up at the specified assessment time. Date of study discontinuation will be mapped to the nearest visit date to define the number of expected forms.
- Evaluable forms = subset of expected FACT-O forms with at least one subscale that can be determined; or where REVPRDI form is ticked 'Subject too heavily affected by symptoms of disease under investigation'.

Thus the overall compliance rate is defined as the number of patients with an evaluable baseline and at least one evaluable follow-up form (as defined above), divided by the number of patients expected to have completed at least a baseline FACT-O form.

Date 15 February 2022

Compliance over time will be calculated separately for each visit, including baseline, as the number of patients with an evaluable baseline form and a form at the time point (as defined above), divided by number of patients still expected to complete forms at that visit. Similarly the evaluability rate over time will be calculated separately for each visit, including baseline, as the number of evaluable forms (per definition above), divided by the number of received forms.

[figure not shown]

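### The FACT-O scoring rule in SAP 3.3.1 does not give its own TOI range of 0-100: read literally it gives 0-876, and read as an average it prorates incomplete forms twice

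*SAP*

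**What the plan says.** SAP 3.3.1 defers to the FACT-O Scoring Manual and then writes out its own steps. Some items are reversed by subtracting the response from 4. Then "scores are summarised and multiplied by the number of items in the domain". For a subscale with less than 50% of its items missing, "the subscale score will be divided by the number of non-missing items and multiplied by the total number of items on the subscale"; with 50% or more missing, the subscale is missing.

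The TOI adds three subscales: "physical well-being (7 items), functional well-being (7 items), and ovarian cancer subscale (11 items) of the FACT-O questionnaire version 4". The resulting scale is given as "The TOI score ranges from 0-100 and the FACT-O from 0-152". A change of 10 points either way defines an improved or worsened visit (SAP Table 5), and Table 6 builds best overall response from those visits. SAP 4.2.9 uses the same score in the MMRM, which is the primary analysis of the FACT-O, and in the AUC analysis.

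**The concern.** The first scoring sentence multiplies by the number of items but never divides by the number answered. The second sentence contains a complete proration. Applied in sequence, the two do not return the stated range.

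The TOI serves a secondary objective, and the 10-point threshold, the MMRM and the AUC are meaningful only on the 0-100 scale. Under the literal rule the damage goes beyond a change of units. The three subscales have different item counts, so they are reweighted against each other, and rescaling the total would not undo that. Someone programming or replicating the endpoint from the SAP has two conflicting instructions.

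**Working it through.** **Inputs (SAP 3.3.1).** Items: physical (PWB) 7, functional (FWB) 7, ovarian subscale 11, so 25 in all. Item range 0-4, inferred from the reversal rule and the stated ranges. Proration factor: items in subscale / items answered. Threshold: 10 points.

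**Stated range, reproduced with plain sums.** PWB 4 × 7 = 28; FWB 4 × 7 = 28; ovarian 4 × 11 = 44. TOI = 28 + 28 + 44 = 100, as stated. The FACT-O maximum of 152 implies 152 / 4 = 38 items, so 13 outside the TOI.

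**Reading A: domain sum × number of items.** With complete data the proration factor is 1.
- PWB 28 × 7 = 196; FWB 28 × 7 = 196; ovarian 44 × 11 = 484.
- TOI maximum = 196 + 196 + 484 = 876, which is 8.76 times the stated 100.
- Ovarian share of the maximum: 484 / 876 = 55.3%, against 44 / 100 = 44% on the stated scale.
- One level on one ovarian item: 1 × 11 = 11 points, above the threshold. One level on one PWB or FWB item: 1 × 7 = 7 points, below it.
- With missing items the maxima do not change. For PWB with 3 of 7 missing: (4 × 4) × 7 / 4 × 7 = 196. The 876 therefore comes from the single multiplication, not from proration.
- With missing items the effect of one level grows. For PWB or FWB it is 7 × 7 / 6 = 8.17 with one missing, 7 × 7 / 5 = 9.8 with two, and 7 × 7 / 4 = 12.25 with three.

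**Reading B: domain average × number of items.** The first sentence now prorates by itself, and the second prorates again.

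| Subscale | Items missing | After first step (max) | After second step (max) | Correct max |
|---|---|---|---|---|
| PWB or FWB | 0 of 7 | 4 × 7 = 28 | 28 / 7 × 7 = 28 | 28 |
| PWB or FWB | 3 of 7 | 4 × 7 = 28 | 28 / 4 × 7 = 49 | 28 |
| Ovarian | 0 of 11 | 4 × 11 = 44 | 44 / 11 × 11 = 44 | 44 |
| Ovarian | 5 of 11 | 4 × 11 = 44 | 44 / 6 × 11 = 80.7 | 44 |

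Three of 7 and 5 of 11 are the largest numbers of missing items that the under-50% condition allows.

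**One proration only.** Sum of answered items × items in subscale / items answered gives maxima of 28, 28 and 44 at every permitted level of missing items, so the TOI stays on 0-100. With complete data one level on any item moves the TOI by 1 point.

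**The case against.** The strongest reply is that the paragraph makes its intention plain. It invokes the Scoring Manual, both stated ranges agree with plain sums of 0-4 items, and output running to 876 would fail the SAP's own range at once. On the averaging reading, complete forms score correctly. The visible protocol text cannot settle the matter, because its PRO derivation (Section 11.3) is blacked out and may contain the right formula. All of this stands as evidence of intent. It does not remove the conflicting instruction: neither reading gives 0-100 at every permitted level of missing items.

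The reply is also right about consequences.
- A reader might infer that one level on any single item would meet the 10-point threshold. With complete data that is true only of the 11 ovarian items, under Reading A; the other 14 move the TOI by 7 points.
- A reader might infer that one such shift would make a responder. It gives only a visit response: best overall response of improved needs two improved visits at least 28 days apart with no worsened visit between them (SAP Table 6).
- The TOI lies outside the alpha-controlled procedure, which covers PFS, PFS2 and OS (SAP 4.2.1).
- FACT-O collection ended at the primary analysis (Protocol 6.5), and this SAP, dated 15 February 2022, treats that analysis as past (Section 5).

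**Conclusion.** The scoring text contradicts its own stated range and should be corrected. Followed literally, it gives a TOI of 0-876 with the ovarian items overweighted by 11/7. With averaging, it overstates subscales that have missing items, by up to 49 / 28 = 1.75 times (PWB or FWB) and 80.7 / 44 = 1.83 times (ovarian).

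It is tempting to conclude that the trial's TOI results were computed on the wrong scale, or that the threshold was set on it. The documents do not support either. They state 0-100, point to the manual, and show no score on any other scale. The simplest explanation is a drafting slip in which the division by items answered was left out of the first sentence.

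The sizes rest on 0-4 items, which the documents imply but do not state; the manual was not available. This is a minor point: it bears on no alpha-controlled endpoint, and what remains is a correction to the text and a check of the code.

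**What to change.** In SAP 3.3.1, delete the multiplication by item count from the sentence on reversed items, and replace the proration sentence with a single formula:

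- Subscale score = (sum of answered, reversed items) × (number of items in the subscale) / (number of items answered), if less than 50% of the items are missing; otherwise the subscale is missing.
- TOI = PWB + FWB + ovarian subscale, range 0-100.

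Keep the explicit 50% condition, since it decides which forms are scored. Then confirm that the TOI program applied this formula once, with no prior multiplication or averaging. The cost is a short text correction and a code check; no new data are needed. Scores would need rederiving only if the check finds a departure.
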